## Study Objectives

Purpose: To determine the outcome differences in patients 6 months and younger with laryngomalacia and dysphagia who are evaluated by speech language therapy (SLP) alone versus those with both SLP evaluation and acid suppression therapy (AST)

Hypothesis: We hypothesize that there will be no differences in outcomes between those that had SLP alone versus those that had both SLP and AST.

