### Methods:

All Department of Pediatric Otolaryngology Airway clinic patients with a referral diagnosis of laryngomalacia will have their medical records screened for eligibility. All eligible families with infants that qualify for the study will be approached the day of clinic by their licensed physician to discuss the study. They will be given the Pittsburgh Airway Symptom Score (PASS) questionnaire and the Infant Gastroesophageal Reflux Questionnaire (I-GERQ-R) at the beginning of the appointment. The physician will then perform the standard procedures at the clinic appointment. The Flexible Laryngoscopy Findings sheet will be filled out in conjunction with the clinic procedures for objective data. The surveys will then be scored to determine true GERD (score  $\geq 16$ ) and severe laryngomalacia (LM) (RED questions on the PASS), which would further exclude these patients. There are 12 total questions on the I-GERQ-R. On the PASS, questions 1 & 2 are in the GREEN category and signifies mild LM, YELLOW signifies moderate LM, and RED is severe LM. On the PASS questionnaire, "Yes" to either #1 or #2 and

nothing else is mild LM, "yes" to at least one #3-5 and none of #6-10 is moderate LM, and "yes" to any of the #6-10" indicates severe LM. There are 10 total questions on the PASS.

Mild and moderate LM patients will be block randomized the day before the appointment to receive speech language therapy alone or speech language therapy with famotidine (Pepcid). Both treatments are standard of care in these patients as well as watchful observation. Speech language therapy is part of the normal clinic visit for LM patients. There is no gold standard of care for LM, therefore this trial is important to establish this. Patients will be randomized in both mild and moderate LM blocks before the appointment, as providers are unaware of the severity until the time of the appointment. After the appointment, if the family does not want to participate, the name will be taken off the randomization sheet completely or off the unused block.

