## Sample Size Calculation

Based on data from Dang et al [1], 62 participants per group will be needed to address the hypothesis that there is no difference in airway symptom improvement between AST and no-AST groups with alpha=.05 and power=.80 (two-tailed Fisher's exact test, G\*Power 3.1). Target enrollment will be 160 participants (80 in the AST group and 80 in the no-AST group, with 40 with mild laryngomalacia and 40 with moderate laryngomalacia in each group) to account for attrition.

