## **Analyses**

Stata/SE 16.1 will be used for all statistical analysis.  
P value < .05 will be used for statistical significance.

Baseline characteristics will be compared between AST and no-AST groups using Chi-squared or Fisher's exact test for categorical data and t-test (normally distributed) or Wilcoxon rank-sum (not normally distributed) for continuous data. Primary outcome measures will be change in LASS and I-GERQ-R scores from initial visit to follow-up and change in airway and dysphagia symptoms assessed by chart review during the 1 year following the initial visit. The LASS and I-GERQ-R scores will be compared between initial and follow-up surveys using Wilcoxon signed-rank tests. Change scores (post-pre) will be calculated for LASS and I-GERQ-R, and differences in the improvement in scores based on laryngomalacia severity or randomization group will be evaluated using Wilcoxon rank-sum tests. Associations between LASS or I-GERQ-R and time between initial and follow-up surveys will be evaluated using Spearman rank correlation. Symptoms and weight at initial and follow-up visits will be compared using McNemar's and Wilcoxon signed-rank tests, respectively. Change in weight percentile based on laryngomalacia severity or randomization group will be evaluated using Wilcoxon rank-sum tests.

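### Two of the four primary outcomes, chart-review airway and dysphagia symptoms, have only a before/after test in Analyses and no comparison between randomized arms

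*Combined protocol and SAP*

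**What the plan says.** The Primary Outcome section lists four outcomes: change in the airway questionnaire score (PASS, called LASS in Analyses), change in I-GERQ-R, and change in the incidence of airway symptoms and of dysphagia symptoms by chart review up to one year. Analyses repeats the last two as primary: "change in airway and dysphagia symptoms assessed by chart review during the 1 year following the initial visit".

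The only test that Analyses gives for symptoms is "Symptoms and weight at initial and follow-up visits will be compared using McNemar's and Wilcoxon signed-rank tests, respectively". Other outcomes are treated differently in the same section:

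- Questionnaire scores: "differences in the improvement in scores based on laryngomalacia severity or randomization group will be evaluated using Wilcoxon rank-sum tests".
- Weight, a secondary outcome: "Change in weight percentile based on laryngomalacia severity or randomization group will be evaluated using Wilcoxon rank-sum tests".
- Fisher's exact test appears once: "Baseline characteristics will be compared between AST and no-AST groups using Chi-squared or Fisher's exact test for categorical data".

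The sample size section rests on a between-arm comparison: "no difference in airway symptom improvement between AST and no-AST groups with alpha=.05 and power=.80 (two-tailed Fisher's exact test". The stated hypothesis is also between arms: "We hypothesize that there will be no differences in outcomes between those that had SLP alone versus those that had both SLP and AST". The Cross-Over section promises an intent-to-treat analysis but names no test.

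**The concern.** Scientific Background gives the reason for the trial: infants improve, and it is not known whether acid suppression or natural resolution is responsible. A before/after test cannot tell these apart. Pooled over arms, McNemar asks whether infants change over time. Run within each arm, it gives two P values, and finding one significant and the other not is not a valid test of the difference between arms. Analyses does not say which of the two is meant.

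Half of the primary outcomes could therefore be reported without a randomized comparison, or with one chosen after the data are seen. For these two outcomes, Analyses states no arm comparison to which the intent-to-treat promise could apply.

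**Working it through.** **1. Tests stated for each outcome.**

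| Outcome | Before/after test in Analyses | Between-arm test in Analyses | Between-arm test elsewhere |
|---|---|---|---|
| PASS/LASS (primary) | Wilcoxon signed-rank | rank-sum on change | – |
| I-GERQ-R (primary) | Wilcoxon signed-rank | rank-sum on change | – |
| Airway symptoms, chart review (primary) | McNemar | none | Fisher's exact, in Sample Size Calculation, if that outcome is this one |
| Dysphagia symptoms, chart review (primary) | McNemar | none | none |
| Weight (secondary) | Wilcoxon signed-rank | rank-sum on change in percentile | – |

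The two symptom primaries are the only rows without an arm comparison in Analyses.

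**2. The plan's own figure.** The 62 per group cannot be reproduced, because the documents give no improvement rates. By exact enumeration, a two-tailed Fisher test at 62 per group has 80% power for assumed pairs such as 95% vs 77%, 80% vs 55%, 50% vs 24.5% and 30% vs 9%, that is, differences of about 18 to 26 points. The finding does not depend on this figure.

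**3. Illustration of the stated test.** All rates are assumptions, with one yes/no result per infant. Let b be the probability of going from symptomatic to symptom-free, and c the reverse. The probability that exact McNemar is significant is the sum over d of Bin(d; n, b+c) × Σ Bin(x; d, b/(b+c)), the inner sum taken over those x whose two-sided binomial P is below .05.

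Assume 60% symptomatic at baseline, so b = 0.60 × resolution rate. Onset is either 10% of asymptomatic infants (c = 0.40 × 0.10 = 0.04) or 10% of all infants (c = 0.10).

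| Resolve | Onset | b, c | n=62 (one arm) | n=124 (pooled) | Exactly one arm significant, arms identical: 2p(1−p) |
|---|---|---|---|---|---|
| 30% | of asymptomatic | 0.18, 0.04 | 0.589 | 0.913 | 0.484 |
| 50% | of asymptomatic | 0.30, 0.04 | 0.959 | 0.9997 | 0.079 |
| 30% | of all | 0.18, 0.10 | 0.159 | 0.327 | 0.267 |
| 50% | of all | 0.30, 0.10 | 0.652 | 0.942 | 0.454 |

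So a pooled McNemar can be significant in most trials with no treatment effect. Comparing within-arm P values can suggest a difference between identical arms in 8% to 48% of trials.

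Now let resolution truly differ by about 26 points. Both arms are significant with probability p1 × p2:

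- Onset in asymptomatic infants: 30% vs 55.8% gives 0.589 × 0.983 = 0.579; 40% vs 65.8% gives 0.848 × 0.997 = 0.845.
- Onset in all infants: 0.159 × 0.773 = 0.123 and 0.395 × 0.909 = 0.359.

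A real difference can therefore be hidden behind two significant results.

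**4. The between-arm alternative.** At 62 per arm with equal improvement rates of 30/40/50/60/70%, the exact Fisher test rejects with probability 0.032/0.035/0.038/0.035/0.032. The Newcombe 95% half-width for a zero risk difference is √[(p−l)² + (u−p)²], where l and u are the Wilson limits. It is 0.158 (30% or 70%) to 0.171 (50%) at 62 per arm, and 0.140 to 0.151 at 80 per arm.

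**The case against.** For airway, the same combined document already names the arms, the outcome, the test, alpha and power in the sample size section, so a reader can infer the intended analysis. Parent-reported airway symptoms also have a between-arm rank-sum test. On this view the complete gap is dysphagia alone. This stands in part: airway is a failure to carry a test over, and dysphagia is an outright omission. But the sample size section does not say whether its airway outcome is the chart-review one or a dichotomized questionnaire score. On either reading, Analyses gives the chart-review outcome no arm comparison.

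The 60% baseline fits airway poorly. All infants have laryngomalacia, and stridor and noisy breathing are among the listed symptoms, so nearly all may be positive at consult. This also stands. With 90% symptomatic, onset in 10% of asymptomatic infants and 30% resolving, within-arm McNemar is significant with probability 0.995. One arm alone is then significant in only 2 × 0.995 × 0.005 ≈ 1% of trials. The 8% to 48% range should not be applied to an airway composite of that kind. The main point survives, because McNemar is then almost always significant whether or not the arms differ.

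The 26-point difference is among symptomatic infants. Over all infants at 60% baseline it is about 15 points (0.60 × 30% = 18% vs 0.60 × 55.8% = 33.5%; or 24% vs 39.5%), where Fisher's power at 62 per arm is about 43% or 39%. The replacement test is valid but not automatically well powered.

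Finally, the choice of visit and the combining of symptoms are endpoint-definition gaps in their own right. They belong here because no between-arm test can be run until they are settled.

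**Conclusion.** The concern holds with high confidence, and it must be fixed. As written, Analyses cannot test the trial's hypothesis for two of its four primary outcomes. This follows from the text alone and from what McNemar's test compares. It does not depend on the illustrative rates. Those rates show only that the stated test can mislead in either direction, by an amount that depends on unknown symptom prevalence, resolution and onset. The link between the sized airway outcome and the chart-review outcome is probable but not stated.

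**What to change.** Amend Analyses as follows.

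1. For airway and dysphagia separately, define improvement as yes/no per infant at a stated follow-up within the year. One example is fewer of the listed symptoms (six airway, four dysphagia) than at consult. Say how infants with no symptom at baseline are counted.
2. Compare randomized arms on each outcome by intent-to-treat, with the Fisher's exact test used for sizing. Alternatively, use a logistic model adjusted for the mild/moderate stratum, since Methods says "Patients will be randomized in both mild and moderate LM blocks before the appointment", and for baseline status where it varies. Report the risk difference with its 95% CI.
3. Keep McNemar as a description of change over time.
4. State whether the airway outcome so defined is the one that was sized. The 62 per group with 80% power stands only if definition and rates match those behind that calculation; otherwise re-check it.

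The cost is SAP wording and a few lines of Stata, with no new data collection. For improvement rates of 30% to 70%, expect a 95% CI for the risk difference of about ±16 to 17 points at 62 per arm, or ±14 to 15 points if all 80 per arm are analysed.

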## **Eligibility Criteria**

### **Inclusion:**

- Pediatric patients ages 0 to 6 months who do need meet the criteria at the initial appointment for supraglottoplasty
- Seen in UPMC CHP Otolaryngology Department
- Laryngomalacia without prolonged (>20 seconds) cyanosis, apnea, nor failure to thrive.

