## Secondary Outcomes

- Weight (kg) From Consult up to 1 Year.
  - Weight change in kilograms assessed from medical chart review from consult up to 1 year
- Number of Participants With the Need for Supraglottoplasty Surgery (Escalation of Treatment) up to 1 Year.
  - The need for escalation of treatment with supraglottoplasty surgery will be assessed through medical chart review up to 1 year.

- Number of Participants With the Need for Acid Suppression Therapy Medication (Famotidine) From Speech Language Therapy Alone Group From the Day After the Consult up to the 3 Month Follow up Appointment.
  - The speech language therapy alone group will be assessed for the need for a prescription for acid suppression therapy (famotidine) from the day after the consult up to 1 year.
- Number of Participants With Each Type of Laryngomalacia (Types 1-3) Found on the Flexible Laryngoscopy Procedure at the Consult.
  - All patients will be scoped with a flexible laryngoscopy at the initial consult and the type of laryngomalacia (Types 1-3) will be noted.
- Number of Participants With the Need for a Different Acid Suppression Therapy Medication (Other Than Famotidine) From the Day After the Consult up to the 3 Month Follow up Appointment.
  - Both groups will be assessed for the need for a different acid suppression therapy medication (other than famotidine) from the day after the consult up to the 3 month follow up appointment.

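### Arms are compared on change in weight percentile, which compresses gains in small infants and costs some power; weight-for-age z-scores avoid this at almost no cost

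*Combined protocol and SAP*

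**What the plan says.** Weight is a secondary outcome. The Secondary Outcomes section defines it as "Weight change in kilograms assessed from medical chart review from consult up to 1 year".

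The Analyses section contains two weight analyses. The first compares visits, not arms: "Symptoms and weight at initial and follow-up visits will be compared using McNemar's and Wilcoxon signed-rank tests, respectively". The second compares randomization groups, and also severity groups: "Change in weight percentile based on laryngomalacia severity or randomization group will be evaluated using Wilcoxon rank-sum tests". The threshold for all tests is "P value < .05 will be used for statistical significance".

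The plan mentions no weight z-score, names no growth reference, and gives no effect size, standard deviation or power for weight. The Sample Size Calculation concerns airway symptom improvement only.

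Eligibility bears on how many very small infants can enter. Inclusion requires "Laryngomalacia without prolonged (>20 seconds) cyanosis, apnea, nor failure to thrive", and infants born before 37 weeks are excluded. Failure to thrive is not defined.

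**The concern.** A percentile is the normal distribution function applied to a z-score, so it is steep in the middle and flat in the tails. Equal growth in SD units gives a large percentile change in an average-sized infant and a small one in a light infant.

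Using a rank test does not remove this. A rank-sum test is unaffected by a monotone transformation of the variable being ranked, but change in percentile is not a monotone function of change in z when baselines differ. The distortion therefore reaches the ranks.

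At stake is the sensitivity of the randomized growth comparison in infants with feeding symptoms. The trial's hypothesis is that the arms do not differ, so an avoidable loss of power leans towards the hypothesized answer and cannot be treated as conservative.

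**Working it through.** **Plan's own figure.** The plan states that "62 participants per group will be needed to address the hypothesis". The response rates behind it are not given, so 62 cannot be reproduced, and it does not concern weight. The step from 62 to 80 per arm implies attrition of 1 - 62/80 = 22.5%. I use 62 per arm below as the evaluable number, with a two-sided rank-sum test at 0.05.

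**Compression.** Percentile = 100 × Φ(z). For a gain of 0.5 SD:

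- from z = 0: Φ(0.5) - Φ(0) = 69.1% - 50.0% = 19.1 points
- from z = -1: Φ(-0.5) - Φ(-1) = 30.9% - 15.9% = 15.0 points
- from z = -2: Φ(-1.5) - Φ(-2) = 6.7% - 2.3% = 4.4 points

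**Effect on ranks.** Infant A moves from z = -2 to -1.5, and infant B from z = 0 to 0.2. On z-score change A ranks higher (0.5 against 0.2). On percentile change B ranks higher, because Φ(0.2) - Φ(0) = 57.9% - 50.0% = 7.9 points against 4.4.

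**Power by simulation.** The same simulated infants are tested on both scales. Assumptions not in the documents: baseline z normal with SD 1.1 and the mean shown; SD of z-score change 0.7; effect either 0.35 SD in every infant or 0.8 SD only in infants with baseline z below -1. The cut removes infants below the 5th percentile (z = -1.645), as a stand-in for the failure-to-thrive exclusion.

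| Effect | Baseline mean z | Cut at 5th percentile | Power, z change | Power, percentile change | Loss (points) |
|---|---|---|---|---|---|
| Uniform 0.35 SD | -0.7 | yes | 76% | 72% | 4 |
| Uniform 0.35 SD | -0.7 | no | 76% | 69% | 7 |
| Uniform 0.35 SD | -1.5 | no | 77% | 66% | 11 |
| 0.8 SD, only z < -1 | -0.7 | yes | 28% | 20% | 8 |
| 0.8 SD, only z < -1 | -0.7 | no | 59% | 36% | 23 |

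Repeat runs moved single entries by up to about 3 points.

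**Other assumptions** (baseline SD 1, 62 per arm):

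- Uniform effect, no cut: about 79% against 73% at mean z 0 or -0.5 (a loss of 6). To regain 79% on the percentile scale takes about 71 to 74 per arm for mean z 0 to -1, and about 83 at -1.5.
- Uniform effect with the cut: about 79% against 75% to 77%.
- Effect of 0.6 SD only below z = -1, with the cut: 23% against 16% (mean z -0.5) and 47% against 35% (mean z -1).
- Effect of 0.5 SD only below z = -1, no cut, change SD 0.5: 34% against 20% (mean z -0.5) and 72% against 44% (mean z -1).

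**Type I error.** With no effect, both scales rejected in about 4.7% to 4.9% of simulated trials.

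**How realistic the uncut baselines are.** The share below the 5th percentile is Φ((-1.645 + 0.7)/1.1) = Φ(-0.86), about 20%, at mean -0.7, and Φ((-1.645 + 1.5)/1.1) = Φ(-0.13), about 45%, at mean -1.5. Both are hard to square with a trial that excludes failure to thrive.

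**The case against.** The strongest reply is that eligibility removes much of the tail in which compression is severe. That stands: with the 5th-percentile cut, the uniform-effect loss is only about 4 points. The cut is itself an assumption, since the plan does not define failure to thrive, but leaving it out overstates the problem.

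A reader might take 59% against 36% as the loss this trial faces. The documents do not support that. It needs a 0.8 SD benefit with a sharp threshold at z = -1, about 39% of infants below that threshold (Φ((-1 + 0.7)/1.1) = Φ(-0.27)), and no thinning of the low tail. With the cut, the z-score test itself has only 28% power, so changing the scale would not rescue that comparison.

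A reader might also infer that the test fails specifically among small infants. Within a narrow band of baselines (z from -2 to -1), power was 79% on z and 76% on percentile. Much of the loss comes from pooling infants with different starting weights.

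Nor does this undermine the trial's main conclusion. Weight is secondary, and the sample size was not set for it.

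Finally, the mismatch between a kilogram outcome and a percentile analysis is the more basic defect. This is fair: if the sponsor chose to compare arms in kilograms, the percentile question would fall away, and changing only the Analyses sentence would replace one mismatch with another. Reconciling the two by keeping percentiles, however, would leave the compression in place.

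**Conclusion.** The point holds as a modest loss of efficiency on one secondary outcome for which no power is stated. The compression and its effect on ranks follow from arithmetic. The size does not, because the documents give no baseline weight distribution, variability or expected effect.

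Under the stated assumptions, a uniform effect loses about 4 points of power with the failure-to-thrive cut and about 6 to 11 without it. An effect confined to small infants loses about 8 points with the cut at baseline mean z -0.7, and about 23 without it as an upper scenario. The planned test is valid: its false-positive rate is not raised. This is a cheap improvement, not a flaw that puts the trial's primary results in doubt.

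**What to change.** In the Analyses section, replace the percentile comparison with this: change in weight-for-age z-score will be compared between randomization groups, and between severity groups, by Wilcoxon rank-sum test. Z-scores will be computed from the recorded weights using one named growth reference for all infants, by sex and exact age at each weighing. Percentiles and kilograms will be reported descriptively.

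In Secondary Outcomes, redefine the weight outcome as change in this z-score, so that outcome and analysis agree.

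Compute from the raw chart weights, because charted percentiles may be rounded or floored at the low end.

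The cost is a sentence or two in each section. The lookup by age and sex that gives the percentile also gives the z-score, so no extra data, visits or participants are needed. The one drawback is that z-scores are less familiar to clinicians, which the descriptive percentiles address.

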### **Cross-Over**

Intent-to-treat analysis will be performed.

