These patients will then be re-evaluated at their follow up appointment in 1 to 4 months. The families will take the PASS and I-GERQ-R surveys again to determine LM severity. If Pepcid is discontinued due to intolerance of side effects, they will be kept in the study in the same arm. If the family opts out of the follow-up appointment or they do not need to follow-up in-person, families will take the post surveys via REDCap or by mail. A REDCap link will be sent along with a letter to the caregivers to the caregivers' email address on file. If the families do not fill out the surveys within 2 weeks, paper copies of the surveys along with a letter to the caregivers will be sent to the caregivers' home address on file. If the families do not return the paper copy or the electronic copy of the surveys, researchers will call the participants for a reminder and will ask if the family wants another paper copy or survey link. The family may also answer the survey questions over the phone.

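### Intent-to-treat is the only planned analysis for a no-difference hypothesis, although stopping and starting famotidine are both foreseen; a pre-specified supportive per-protocol analysis is missing

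*Combined protocol and SAP*

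**What the plan says.** All references are to the combined protocol and SAP.

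- **Hypothesis.** Study Objectives: "We hypothesize that there will be no differences in outcomes between those that had SLP alone versus those that had both SLP and AST". The Sample Size Calculation addresses "the hypothesis that there is no difference in airway symptom improvement between AST and no-AST groups", "with alpha=.05 and power=.80 (two-tailed Fisher's exact test").
- **Size.** The same section says "62 participants per group will be needed". It raises enrolment to 80 per group for attrition; cross-over is not mentioned.
- **Stopping.** Methods, in the follow-up paragraph: "If Pepcid is discontinued due to intolerance of side effects, they will be kept in the study in the same arm".
- **Starting.** Secondary Outcomes counts SLP-alone infants who need famotidine, and infants in either group who need another acid suppressant. For famotidine in the SLP-alone group, the outcome's title ends the window at the 3 month follow-up, while its description runs to 1 year.
- **Analysis.** The Cross-Over section consists of "Intent-to-treat analysis will be performed". The Analyses section uses difference tests at P < .05. No equivalence or non-inferiority margin is stated, and no per-protocol, as-treated or complier analysis is named.

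**The concern.** In a trial that seeks a difference, intent-to-treat is conservative, because departures from allocation usually shrink the estimate. Here the hypothesised result is the absence of a difference, so the same shrinkage works towards the hypothesis. Departures are foreseen in both arms, yet the counts of them enter no efficacy comparison and no second analysis would show whether they mattered.

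The Scientific Background says the study should help to set guidelines for mild and moderate laryngomalacia. If AST has a real effect and cross-over blurs it, a non-significant result could be carried into practice as evidence that AST adds nothing.

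**Working it through.** **Inputs from the documents.** 62 evaluable per group, 80 enrolled per group, two-sided alpha .05, power .80, Fisher's exact test (all from Sample Size Calculation).

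**Inputs that must be assumed.** The response rates and the rates of stopping and starting are not given. I take the higher response rate from 0.50 to 0.90, place it in the AST arm, and use two illustrative pairs of departure rates.

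**The plan's own figure.** 62 per group cannot be reproduced without response rates, and nothing here shows it to be wrong. Solving backwards by full enumeration, the smallest whole-point difference with at least 80% power at 62 per arm is 26 points (higher rate 0.50 to 0.75), 25 points (0.80) or 22 points (0.90). On enrolment, 1 - 62/80 = 0.225 and 62/(1 - 0.225) = 80, so the increase from 62 to 80 equals a 22.5% allowance. The plan assigns that to attrition, which leaves nothing for cross-over.

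**Dilution model.** Let pA and pS be the response rates under full adherence and d = pA - pS. If a share s of the AST arm stops and a share c of the SLP-alone arm starts, and each change removes or adds the whole effect, then:

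- AST arm: qA = pA - s × d
- SLP-alone arm: qS = pS + c × d
- Intent-to-treat difference: qA - qS = (1 - s - c) × d

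Example with pA = 0.70 and pS = 0.44, so d = 0.26:

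- s = 0.10, c = 0.10: 0.674 against 0.466, difference 0.80 × 0.26 = 0.208
- s = 0.15, c = 0.20: 0.661 against 0.492, difference 0.65 × 0.26 = 0.169

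**Power.** This is the sum, over all outcome pairs for which the two-sided Fisher test rejects, of the product of the two binomial probabilities, with 62 per arm.

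| pA | pS | d | No departures | 10% stop + 10% start | 15% stop + 20% start |
|---|---|---|---|---|---|
| 0.50 | 0.24 | 0.26 | 81.8% | 61.2% | 42.9% |
| 0.60 | 0.34 | 0.26 | 80.6% | 60.4% | 42.8% |
| 0.70 | 0.44 | 0.26 | 80.8% | 60.5% | 42.7% |
| 0.80 | 0.55 | 0.25 | 80.9% | 59.9% | 42.2% |
| 0.90 | 0.68 | 0.22 | 82.1% | 60.3% | 42.3% |

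One minus these figures is the chance of a non-significant result when AST works: 18-19% with no departures, 39-40% with 10% + 10%, and 57-58% with 15% + 20%.

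**Sensitivity.** Whole-point differences start slightly above 80%. Starting from exactly 80%, power is 58-60% and 40-42% in the two scenarios. If all 80 per arm were evaluable, with the same effect, it would be 69-72% and 50-53%.

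**The case against.** The strongest reply is that intent-to-treat fits the question. Two standard-of-care strategies are compared, so later famotidine in the SLP-alone arm can be seen as part of that strategy, and keeping infants who stop in their arm is deliberate. If SLP-alone infants needed rescue because AST works, the planned count of famotidine prescriptions would partly show it. This stands as a reason to keep intent-to-treat first. It does not remove the gap, because no test is attached to that count and it is not linked to the efficacy result.

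A second reply is that the root problem is the missing margin: a non-significant difference test does not establish no difference even with perfect adherence. That is correct, and dilution aggravates it. But a margin alone would not cure dilution. With an assumed margin of 0.10 to 0.20, a higher rate of 0.70 or 0.80, a true difference equal to the margin and 62 per arm, the normal approximation puts the chance of falsely concluding non-inferiority at 4.2-7.1% with 10% + 10% departures, against a nominal 2.5%.

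A third reply is that dilution is not certain, which also stands. Cross-over by need depends on outcome, and the effect gained or lost may be partial. Questionnaire outcomes are analysed in completers without imputation, which can bias either way.

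A reader might also infer three stronger things that the documents do not support:

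- That substantial cross-over is expected. The text provides for it but gives no rate.
- That intent-to-treat is a wrong choice, or was chosen to reach a preferred answer. It is a sound main analysis, and the documents state a hypothesis, not a motive.
- That all primary outcomes are affected alike. PASS and I-GERQ-R are repeated at 1 to 4 months, so later departures cannot dilute them, and no loss has been worked out for their rank-sum comparisons.

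**Conclusion.** The concern holds in a limited form. With a no-difference hypothesis, foreseen departures in both arms and intent-to-treat as the sole analysis, any dilution favours the hypothesised conclusion, and the plan has no means of showing whether it occurred.

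Its size is unknown. Under the assumed rates, power drops from about 80% to about 60% (10% + 10%) or about 42-43% (15% + 20%) for the binary endpoint behind the sample size. This rests on the assumed response rates and on starting or stopping famotidine adding or removing its full effect. The remedy is a supportive analysis and a rule for wording the conclusion, not a replacement for intent-to-treat.

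**What to change.** 1. Keep intent-to-treat as the main analysis.
2. Add a pre-specified supportive per-protocol analysis of the between-arm comparisons, with adherence to allocated treatment up to each outcome assessment defined in advance.
3. Record when AST infants stop famotidine, and report stopping and cross-over by arm.
4. Reconcile the two windows in Secondary Outcomes for famotidine use in the SLP-alone group, so that cross-over has one definition.
5. State that a non-significant intent-to-treat result alone will not be reported as showing no difference, but will be given with its confidence interval and the per-protocol result.

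A complier-average estimate is optional. It assumes that allocation affects outcome only through famotidine, which is doubtful here because no blinding is described and two primary outcomes are parent-reported.

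**Cost.** SAP wording, one extra set of analyses and one new data item: new prescriptions are already counted, but no listed outcome captures when famotidine is stopped. The downside is that per-protocol results are open to selection bias, so they can only support the main analysis.
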